prevalence of undiagnosed and uncontrolled hypertension at Cedars-Sinai is high, slow uptake of these new standards may be one explanation. However, another potential explanation is the much greater level of effort needed to attain the lower blood pressure goals. If clinicians are recognizing uncontrolled hypertension and initiating or intensifying treatment, we would expect the time-to-care measures to exhibit stable performance after 2017 while performance on the time-to-control measures and cross-sectional control rates would decline.

We will also examine how performance on the time-to-care and time-to-control measures varies based on the setting in which blood pressure is measured. If we find that that performance on these time-to-care and time-to-control measures as well as control rates are better in Primary Care, Internal Medicine, Nephrology, or Cardiology clinics than in other specialty and subspecialty clinics, this would suggest the EMR may be a useful for the screening and detection of patient populations that would benefit from efforts to make a diagnosis and initiate or intensify treatment.

Aim 3B – We will perform a pilot study of the new time-to-control measure’s responsiveness to more intensive blood pressure monitoring and intervention. This pilot will provide a subset of uncontrolled hypertensive patients with home blood pressure monitors linked to the EMR at Cedars-Sinai. This information will be monitored and acted upon weekly, allowing for a more rapid titration of medical therapy. A decrease in the time-to-control measure of blood pressure management would be a preliminary finding consistent with measure responsiveness.

Aims 4A and 4B: Aim 4A – We will conduct interview discussions to explore feasibility and acceptability of text message reminder and incentives for blood pressure medication adherence. These interview discussions will involve both patients and providers and will allow for a better understanding of existing routine behaviors that support pill-taking, appropriate messaging for text message reminders, and how to best implement the intervention.

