We will create three time-to-care measures: time-to-diagnosis, for patients who qualify for new diagnoses; time-to-initiate, for the same patients; and time-to-intensify, for patients with established diagnoses. We will create two time-to-control measures, one for patients with new and one for patients with established diagnoses. The new time-to-care and time-to-control measures will be based on the 2017 ACC/AHA guidelines. We will define undiagnosed hypertension as two ambulatory blood pressures \geq 130/80 without an ICD-9/10 code for hypertension in the preceding year; uncontrolled hypertension will be defined using the same blood pressure criterion but patients will have an ICD-9/10 code for hypertension. A new diagnosis of hypertension will be defined as an ICD-9/10 code for hypertension without a prior code or antihypertensive medication use in the preceding year. We will define treatment initiation as the first prescription for an antihypertensive medication following a new diagnosis of hypertension. Treatment intensification will represent the addition of another antihypertensive medication, an increase in the dose of an existing antihypertensive medication, and a change from one antihypertensive medication to another. We will access the 2017 guidelines and other standard sources to develop a list of antihypertensive medications. Time to care will be calculated as the number of days from the last blood pressure above goal to the documentation of the diagnosis or the initiation/intensification of treatment. Time to control will be calculated as the number of days from the last blood pressure above goal to the first blood pressure at goal.

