7.0 STATISTICAL CONSIDERATIONS

7.1 STUDY OUTCOME MEASURES

Analyses will test the following pre-specified hypotheses for each goal:

Aim	Hypotheses
1: Determine cross-sectional prevalence of undiagnosed and uncontrolled hypertension at CSMC, as well as the patient, physician, and clinic characteristics associated with these outcomes.	
 1) Cross-sectional rates of undiagnosed and uncontrolled hypertension at CSMC, based on the 2017 AA/AHA Guidelines, will be similar to national rates (20% and 50%, respectively). 2) Cross-sectional rates of undiagnosed and uncontrolled hypertension will be higher under the 2017 ACC/AHA Guidelines than the JNC-7 Guidelines. 3) Rates of undiagnosed and uncontrolled hypertension will be lower among patients with visits in Primary Care, Internal Medicine, Nephrology, or Cardiology clinics than for patients who only receive care in other clinics.
2: Develop and pilot test new time-to-care and time-to-control measures.	
 1) Data already collected in the EMR can be used to calculate these five new measures of hypertension care.
3A: Assess the validity, responsiveness, and potential utility of the new time-to-care and time-to-control measures.	
 1) Performance on the time-to-care and time-to-control measures will be associated with cross-sectional control rates at the clinic and physician level. 2) Following release of the 2017 ACC/AHA Hypertension Guidelines, performance on the time-to-control measures and cross-sectional control rates will worsen while performance on time-to-care measures will remain stable. 3) Performance on the time-to-care and time-to-control measures will be better for patients with visits in Primary Care, Internal Medicine, Nephrology, and Cardiology clinics than for patients who only receive care in other clinics.

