For Aim 3A, we will conduct unadjusted and then adjusted multivariate regression analyses assessing whether time-to-care and time-to-control measures are predictors of (i.e., associated with) blood pressure control rates at the physician level. We will perform these analyses at the physician and clinic levels because time-to-control rates are tautologically associated with the presence of control, and because many types of future quality improvement interventions would likely target individual physicians and clinics. We will compare performance on these measures and control rates between patients with visits in Primary Care, Internal Medicine, Nephrology, and Cardiology clinics than for patients who only receive care in other specialty and subspecialty clinics.

Next, we will perform interrupted time-series analyses of changes in the three hypertension measures after 2017 using multivariate regression models. These analyses will examine each hypertension measure (time-to-care, time-to-control, and control rates) as the dependent variable, using the quarter year as the independent variable. We will examine whether there is a change in intercept or slope during any quarter following the announcement of the ACC/AHA guidelines in 2017. We will then qualitatively compare such changes across the three outcome measures, to assess whether time-to-care is more responsive, as expected.

For Aim 3B, we will conduct unadjusted and then adjusted multivariate regression analyses assessing whether time-to-control measure was different between those enrolled in the pilot study and patients in the non-intervention group.

For Aim 4A, two independent coders will develop a codebook that details the inclusion and exclusion criteria, as well as typical exemplars for each topic or theme. Together, the coders will work to establish inter-coder reliability (evidenced by Cronbach's alpha $\geq .70$) with the goal to converge on a single, agreed upon meaning for each thematic area. For each topic, they will identify the range of themes mentioned, which were most and least salient, and which were discussed most and least frequently. This will produce research reports on specific topics describing the range, central tendency, and distribution of each theme, presenting segments of text as exemplars, which will be used to guide the refinement and implementation of the intervention in Aim 4B.

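### The clinic-setting comparison is posed by where blood pressure was measured but planned by patients' visit history, so visits after the high reading can decide the group

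*Protocol*

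**What the plan says.** **The question.** Protocol Section 2.0 (Aim 3A) says the investigators will examine how performance on the time-to-care and time-to-control measures "varies based on the setting in which blood pressure is measured". If the four clinic types do better, "this would suggest the EMR may be a useful for the screening and detection of patient populations" who would gain from diagnosis or treatment.

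**The planned comparison.** The Aim 3A analysis text in Section 7.1 reads: "We will compare performance on these measures and control rates between patients with visits in Primary Care, Internal Medicine, Nephrology, and Cardiology clinics", set against "patients who only receive care in other specialty and subspecialty clinics". Aim 3A hypothesis 3 has the same form: "Performance on the time-to-care and time-to-control measures will be better for patients with visits in Primary Care, Internal Medicine, Nephrology, and Cardiology clinics", with the comparison group again being those whose care is confined to other clinics. Aim 1 hypothesis 3 applies the split to prevalence: "Rates of undiagnosed and uncontrolled hypertension will be lower among patients with visits in Primary Care, Internal Medicine, Nephrology, or Cardiology clinics", again compared with patients who attend only other clinics.

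**The clock.** Section 4.0 anchors the time measures to a reading: "Time to care will be calculated as the number of days from the last blood pressure above goal to the documentation of the diagnosis" or to treatment initiation or intensification. The clinic where that reading was taken plays no part in the grouping.

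Neither document gives a window, an index visit or a rule for patients seen in both kinds of clinic. The SAP covers only the adherence trial and is silent on this comparison.

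**The concern.** The question concerns a property of a reading: the clinic in which it was taken. The grouping concerns a property of a patient: which clinics appear in the record. The two agree for patients whose high reading was taken in one of the four clinic types. They can disagree for everyone else.

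Take a patient found high in ophthalmology who sees an internist a year later. By setting of the reading, this is an ophthalmology case. By the planned split, the patient belongs with the four clinic types. A similar patient who never sees an internist stays in the other group. Group membership is then fixed partly by what happens after the reading. Because the later visit may bring about the diagnosis, or be prompted by it, membership can carry information about the outcome.

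At stake is the screening inference in Section 2.0. A gap between the groups could arise from who went on to attend the four clinic types, and not from how high readings are handled where they are taken.

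**Working it through.** The documents state no sample size, effect or power for this comparison, so there is no figure to reproduce. The check compares the texts, then illustrates the mechanism with assumed inputs.

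**1. How much room there is for later visits.** Section 4.0 requires clinic visits at least two years apart. Study dates run to 30 March 2019, from 1 January 2014 in Section 4.0 or 1 January 2012 in Sections 3.2 and 5.2. Each patient's record therefore spans at least two years, over which a visit to one of the four clinic types can follow a high reading.

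**2. Illustration (all inputs assumed).**
- a = share of high readings taken in the four clinic types
- r = chance of a later visit there when the reading was taken elsewhere
- dR, d0 = chance of later diagnosis with and without that visit
- dA = chance of diagnosis when the reading was taken in the four clinic types

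By setting of reading: dA versus B, where B = r·dR + (1 − r)·d0.

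By the planned split: [a·dA + (1 − a)·r·dR] / [a + (1 − a)·r] versus d0.

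With a = 0.5, r = 0.4, dR = 0.7, d0 = 0.1 and no true difference by setting:
- B = 0.4 × 0.7 + 0.6 × 0.1 = 0.34, and dA is set to 0.34.
- Planned split: (0.5 × 0.34 + 0.5 × 0.4 × 0.7) / (0.5 + 0.5 × 0.4) = 0.31 / 0.70 = 44.3%, versus 10.0%.
- Share of the with-visits group whose reading was taken elsewhere: 0.20 / 0.70 = 28.6%.

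Differences in percentage points, with a = 0.5 and r = 0.4 throughout:

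| dR, d0 | No true difference: by setting | No true difference: planned split | dA = 0.6: by setting | dA = 0.6: planned split |
|---|---|---|---|---|
| 0.7, 0.1 | 0 | +34.3 | +26.0 | +52.9 |
| 0.5, 0.3 | 0 | +11.4 | +22.0 | +27.1 |
| 0.4, 0.4 | 0 | 0 | +20.0 | +14.3 |
| 0.3, 0.4 | 0 | −5.7 | +24.0 | +11.4 |

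Over a from 0.3 to 0.7 and r from 0.2 to 0.6, with no true difference, the planned split gave +5 to +50 points when dR > d0, zero when dR = d0, and −3 to −8 points when dR = 0.3 and d0 = 0.4. The share of the with-visits group whose reading was elsewhere ranged from 8% to 58%.

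**3. Diagnosis prompting the visit.** A simulation of 400,000 patients over 730 days placed all readings elsewhere and gave the later visit no effect on diagnosis. With median times of 365 days to both diagnosis and visit, and the visit rate tripled after diagnosis, 78.9% of those who ever attended were diagnosed, versus 42.5% of those who never did. When visits were independent of diagnosis, the figures were 75.0% versus 74.8%.

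**4. What the illustration does not estimate.** It counts diagnosis after the reading. The plan's measures differ in two ways.
- *Time measures.* Suppose a high ophthalmology reading on day 0 and an internist's diagnosis on day 365. If the internist also records a high reading that day, the last reading above goal is on day 365 and time-to-diagnosis is 365 − 365 = 0 days. If the internist's reading is at goal, it is 365 − 0 = 365 days. The planned split puts the patient with the four clinic types both times.
- *Undiagnosed status.* Section 4.0 looks back one year for a diagnosis code. A patient with two high ophthalmology readings and no code meets the definition then, even if coded later. If that patient later sees an internist, the case can count as undiagnosed within the with-visits group, which works against the hypothesis.

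**The case against.** The strongest reply is that this is an unstated window and not a plan to classify on future visits: Section 7.1 never says *ever*, and grouping on visits up to the reading could be fitted to its words. It is true that no window is stated. But a patient who *only* receives care elsewhere is, on the plain wording, one with no visit to the four clinic types anywhere in the record. An analyst following the text would code it that way.

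Second, Section 2.0 itself commits to looking by setting. Specialty is extracted for each visit (Section 4.0, Table 1), and the Aim 1 regression includes clinic characteristics. This shows that a setting analysis is intended and feasible, so a reader should not infer that the data cannot answer the screening question. It does not supply the analysis: the Aim 1 model does not say which visit's clinic is used and does not cover the time measures.

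Third, a reader might infer that the split must inflate the undiagnosed and uncontrolled rates of the other-clinics group, or must lengthen times in the four-clinic group. The documents support neither. The gap can be zero or reversed, a repeat high reading resets the clock, and undiagnosed status looks backward. This objection stands in full.

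Fourth, comparing patients who reach the four clinic types with those who never do has descriptive value for targeting. That also stands, but it is a different question from where high readings go unaddressed.

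Last, Aims 1 to 3A are preparatory, and Section 7.1 expects the measures to be refined. This lowers the stakes but leaves two pre-specified hypotheses with a grouping that does not match the question.

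**Conclusion.** The point holds as a mismatch between the stated question and the planned grouping. Section 2.0 asks about the setting of the reading. Section 7.1 groups by visit history with no window, so later attendance can decide the group for patients whose high reading was taken elsewhere. Followed as written, the rule can produce a gap where none exists by setting, or distort a real one in either direction.

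The size and direction are not known from the documents. In the assumed cases the artefact often favours the hypothesis, up to +50 points with no true difference, but it is zero when later visits are unrelated to diagnosis and slightly negative in others. These figures concern later diagnosis and do not estimate Aim 1 hypothesis 3 or the time measures. The conclusion rests on reading *only* as covering the whole record. The comparison should be respecified before analysis. The Aim 4B randomised comparison is unaffected.

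**What to change.** In Section 7.1, for Aim 1 hypothesis 3, Aim 3A hypothesis 3 and the Aim 3A analysis text:
- Make the primary setting comparison by the clinic where the relevant reading was recorded. For the time measures, use the reading that starts the clock under Section 4.0. For undiagnosed or uncontrolled status, use the readings that define it, with a mixed category if the two come from different settings.
- Alternatively, group by visits on or before that reading, and state the window.
- Do not use later visits to define the group. Report later attendance at the four clinic types as a step toward diagnosis or control.
- Keep the contrast between patients who ever attend the four clinic types and those who attend only others, if wanted, as a descriptive secondary analysis labelled as such.

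The cost is revised wording and a recode. Specialty, visit dates and readings are already collected for each visit. The downside is a mixed-setting category whose size the documents do not allow one to predict.

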
Research Procedures
	
 • The primary research procedures for Aims 1, 2 and 3A are a retrospective review of blood pressure levels for outpatients in the Cedars-Sinai system before and after the introduction of the new clinical guidelines. • Aim 3B is a pilot study to assess the use of home blood pressure monitoring linked to the electronic medical record. This is a prospective intervention of an already approved device, which is compatible with the Cedars-Sinai electronic medical record system and promoted on the Cedars-Sinai website. Study participants for this feasibility study will only include patients already under the care of the PI. • Aim 4A involves conducting interviews discussions to understand the feasibility and implementation of an intervention to increase medication adherence. Participants in the interviews will include current patients who are taking hypertension medications as well as clinic staff. • Aim 4B is a pilot study to evaluate the feasibility, acceptability, and efficacy of an intervention to increase medication adherence involving text message reminders and small incentives for adherence to pill-taking routines.

Subject Population
	
 • For Aims 1-3: All patients seen at least twice in a 12-month period at any Cedars-Sinai outpatient facility • For Aim 4A: All patients with hypertension currently taking hypertension medication and clinic staff • For Aim 4B: All patients with hypertension taking hypertension medication

Duration	
 • For Aims 1, 2 and 3A, all data is retrospective, using already available data collected during routine care. The data to be utilized was collected as part of clinical care from 1/1/2012 through 3/30/2019. • For Aim 3B, prospective data collection will occur during a 9 week period, beginning at the time of patient enrollment. • For Aim 4A, interviews will last one hour on regular clinic days. • For Aim 4B, prospective data collection will occur during a 9 month period, beginning at the time of patient enrollment.
----------	--

GENERAL INFORMATION

CSMC Co-Investigators	
[name], MS [name]
 
[name] [name]

Sponsor/Funder	NIH/NHLBI
Collaborating Institutions Involved in the Research	
RAND Corporation [name]

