4.0 STUDY DESIGN AND METHODS

Achieving these objectives and aims will involve an analysis of existing data from ambulatory care visits at clinics affiliated with Cedars-Sinai Medical Center from January 1, 2014 through March 30, 2019. Via a detailed study protocol, we will establish patient eligibility criteria, specify study variables and measures for extraction from the EMR, and specify descriptive and multivariate regression analyses

related to Aims 1-3. An Advisory Board consisting of local and national experts in EMR systems, population health, hypertension, and the implementation of quality improvement interventions will provide guidance and feedback on the protocol and after we have obtained preliminary data.

Patients will need to have at least two years of data available in CS-Link to be included in the study (defined as two or more clinic visits at least two years apart and occurring within the study dates). We will include ambulatory care visits with faculty, medical delivery network, and private physicians in all specialties if they use CS-Link. We will exclude care in the emergency department, urgent care, and hospital settings because blood pressure may be temporarily elevated due to acute illness. For eligible visits, we will obtain the recorded blood pressure values, whether the blood pressure was assessed manually or automatically (if available), and the physician identity (coded).

We will define blood pressure control based on the 2017 ACC/AHA guidelines (blood pressure <130/80). In sensitivity analyses, we will also consider control based on the JNC-7 guidelines (blood pressure <140/90), due to the recent change in the standard of care.

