5.2 TIME PERIOD OF DATA UNDER REVIEW

- Data will be reviewed from between the dates 1/1/2012 through 3/30/2019. For patients enrolled in the pilot study described in Aim 3B, data will be collected during the 9 week period of their participation.

- Data for Aims 1, 2 and 3A will be collected retrospectively. For Aim 3B, data will be collected weekly starting on the date of their in-person appointment and will be collected prospectively during the 9 week period of monitoring for each patient, estimated between the months of June and November, 2019. For Aim 4A, data will be collected during the interview discussions. For Aim 4B, data will be once per month during clinic visits for the first 3 months, and then every 3 months until 9 months after enrollment.
- Information will be kept for a total of 2 years following the initiation of the study.

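### The Aim 3A interrupted time series searches every post-guideline quarter for a level or slope change with no error control; at an assumed 0.05 per coefficient, a series with no break shows one about 26–41% of the time

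*Protocol*

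**What the plan says.** Protocol section 7.1 plans "interrupted time-series analyses of changes in the three hypertension measures after 2017 using multivariate regression models". Each model takes "each hypertension measure (time-to-care, time-to-control, and control rates) as the dependent variable", "using the quarter year as the independent variable". The decision step is: "We will examine whether there is a change in intercept or slope during any quarter following the announcement of the ACC/AHA guidelines in 2017". The changes found are then compared qualitatively across the three measures to judge which is the more responsive.

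The hypothesis table in the same section gives the prediction this analysis serves (Aim 3A, hypothesis 2). After the guideline, time-to-control and cross-sectional control rates should get worse, while time-to-care should not change.

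The length of the series depends on which section is read. Section 5.2 says "Data will be reviewed from between the dates 1/1/2012 through 3/30/2019", and the Duration entry in the summary table agrees. Section 4.0 instead describes data "from January 1, 2014 through March 30, 2019".

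Neither document names the interruption quarter, a lag, a significance level for this analysis, a correction for looking at several quarters, or an error structure. The SAP deals only with the adherence trial.

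**The concern.** An interrupted time series draws its strength from a break date fixed in advance. Here the date is left open across every quarter after the announcement, and at each one either of two coefficients may count as a change. That is an unadjusted multiple search. Quarterly clinical series also tend to be autocorrelated, and ordinary regression standard errors are then too small.

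Hypothesis 2 of Aim 3A is a contrast between series that break and a series that does not. A chance break in time-to-care would contradict it when nothing happened. A chance break in time-to-control or control rates would lend it support. The qualitative comparison offers no protection, because its inputs are the breaks that the search has found.

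**Working it through.** The plan gives no error rate, power or sample size for this analysis, so there is no figure of its own to reproduce. The check asks how often the stated rule finds a break when there is none.

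**Inputs from the protocol**
- Series length: 2012 Q1 to 2019 Q1 is 7 × 4 + 1 = 29 quarters; 2014 Q1 to 2019 Q1 is 5 × 4 + 1 = 21 quarters. Both were run.
- Candidate quarters: the protocol dates the event only as "following the announcement of the ACC/AHA guidelines in 2017". Counting from 2018 Q1 to 2019 Q1 gives 5. Including 2017 Q4 gives 6. Placing the announcement in the second quarter of 2017 gives 8.
- Tests per series: one level and one slope test at each candidate quarter, except that slope cannot be estimated at the last quarter. This gives 2 × 5 − 1 = 9 tests for 5 quarters, 2 × 6 − 1 = 11 for 6, and 2 × 8 − 1 = 15 for 8.

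**Assumptions (not in the documents)**
- Two-sided 0.05 for each coefficient, unadjusted.
- Gaussian errors, independent or AR(1).

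**Upper reference.** If the tests were independent, the chance of at least one false positive would be 1 − 0.95^k: 1 − 0.95^9 = 37% and 1 − 0.95^11 = 43%. The tests overlap heavily, so the true rate is lower and needs simulation.

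**Simulation.** In each setting, 20,000 series without a break were generated. At each candidate quarter b the model y = β0 + β1·t + β2·1(t ≥ b) + β3·(t − b)·1(t ≥ b) was fitted by ordinary least squares. A false break is any p < 0.05 for β2 or β3 at any b.

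| Candidate quarters | Independent errors | Autocorrelation 0.3 |
|---|---|---|
| 5 | 26–27% | 33–35% |
| 6 | 30–31% | 39–41% |
| 8 | 37–38% | 50–53% |

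Ranges cover the 21- and 29-quarter series, so the conflicting start dates matter little. At autocorrelation 0.5 with 5–6 quarters the rate is 36–49%.

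**Other readings of the rule** (5–6 quarters, independent errors): joint 2-df F test at each quarter, 15–18%; level change only, 21–26%; slope change only, 15–18%.

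**Alternatives** (5–6 quarters after the break)
- One pre-set break, joint 2-df F test: about 5% with independent errors; 13–15% at autocorrelation 0.3 if it is ignored.
- One pre-set break, level and slope tested separately: 8–9% with independent errors.
- One pre-set break with Newey-West errors: about 33–52%, because there are so few points after the break.
- One pre-set break with AR(1) errors by iterated Prais-Winsten: 9–13% with independent errors and 12–18% at autocorrelation 0.3.
- Search kept, Bonferroni over its 9–11 tests: about 4% with independent errors; 6–8% at autocorrelation 0.3 if it is ignored.

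**The case against.** The best case for the plan has four parts.

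*The protocol states no formal decision rule.* It speaks of examining changes and comparing them qualitatively. This stands to the extent that every rate above is conditional on an assumed test. It does not remove the problem: the sentence says to look in any quarter for either coefficient, and even the milder joint-test reading gives about three times 5%.

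*A false break somewhere is not false confirmation of the hypothesis.* This is right, and a reader might wrongly infer that hypothesis 2 would be falsely confirmed in 26–41% of null analyses. The hypothesis needs two measures to break and the third not to. If the series were independent with per-measure rate p, that pattern would occur with probability p²(1 − p): 0.26² × 0.74 = 5.0% to 0.40² × 0.60 = 9.6%. Requiring worsening in both cuts this to roughly a quarter. The measures are not independent, so these figures only illustrate the point. The damage is more direct on the other side: a time-to-care series that truly did not change would appear to break at the full per-series rate.

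*Slow uptake justifies looking past one quarter.* Section 2.0 does raise slow adoption of the new standards. This is a fair reason for a lagged analysis or a corrected search, but not for an uncorrected one.

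*The data set is very large.* Section 7.2 expects over 2.5 million readings. The break is nevertheless judged on 21 or 29 quarterly points, and more readings within a quarter do not add quarters.

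A reader might also compound the per-series rate over the three measures. The documents do not support that calculation: the measures come from the same patients, and section 7.1 itself notes that time-to-control and control are linked by construction.

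**Conclusion.** The point holds, in conditional form. The stated rule leaves the break date open and uncorrected, and nothing elsewhere in either document closes the gap. The per-series false-break rates of 26–31% (independent errors) and 33–41% (autocorrelation 0.3) rest on three assumptions: two-sided 0.05 for each coefficient, 5–6 candidate quarters, and no correction for autocorrelation. An earlier announcement quarter or stronger autocorrelation raises them; a joint test at each quarter lowers them.

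A reader might take this to undermine Aim 3A as a whole. It does not. The time series serves one of three Aim 3A hypotheses; the association with control rates and the comparison of clinic settings do not use it. Aim 3A is a retrospective pilot analysis, separate from the randomised adherence trial that the SAP covers. The change should be made before the analysis is run.

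**What to change.** In section 7.1, name one interruption, at the quarter of guideline release, and state which quarter that is. For each measure, test level and slope change jointly (2 df) at a stated significance level.

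State how autocorrelation is handled. Take the reference distribution from a small-sample method, such as simulation or a parametric bootstrap under a fitted AR(1) null. Its false-positive rate was not computed here and should be checked at the actual series length before use. Do not use Newey-West errors with so few quarters after the break.

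Name one lagged break as a sensitivity analysis to allow for slow uptake, and show the remaining quarters as descriptive plots only. If the search is to be kept, apply Bonferroni over its 9–11 tests for each measure. Settle the series start date (2012 or 2014) in the same edit.

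The cost is wording and a short simulation; no new data are needed. The downside is that a delayed change is picked up only through the slope term and the named lag, or with less power if the Bonferroni search is kept.
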